## 10. STUDY PROCEDURES

### *Consent, screening and familiarisation (visit 1): fam and hypoxic screen*

Once participants have provided fully informed written consent, they will complete a health history questionnaire including additional questions specific to exercise in a hypoxic environment. This form will be signed off by the Principal Investigator following each participants' responses to the questionnaires to assess eligibility. If there are ANY questionable responses, these will be check by our independent medical officers (medcis whose expertise are in extreme environments) or our diabetes consultant (depending on the nature of the response). Further to this, all participants are required to undertake a spirometry tests and blood pressure assessment, provide a venous blood sample and have a 12 lead ECG carried out. Blood will be sent for analysis and screened for any health complications that may affect their participation in this study including, glycated hemoglobin, sickle anemia, thalassemia, and haemoglobinopathy. Results from the 12 lead ECG will be examined by a clinician as will any health history questionnaires that demonstrate questionable responses.

### *Hypoxic screening and familiarisation*

Participants will be assessed for lung function (FVC and FEV1/FVC ratio, PEF). Participants will undergo a one hour, supine exposure to hypoxia (FIO2 = ~0.155, adjusted based upon oxyhaemoglobin saturation during pilot hypoxic exposure to ensure target SpO2 of ~88-92 %). Participants' desaturation will be recorded. Anyone who desaturates to below 65 % SpO2 or in whom end tidal CO2 or O2 of less than 25 mmHg or 45 mmHg respectfully is recorded. Eligible participants will then be randomly allocated (using randomizer.org) to start in either the hypoxia or sham condition (see details below). Participants will be sent home with a SpO2 (Equivital EQ02, Hidalgo, UK) monitor that will record oxygen saturation for 2 nights so that we can screen for undiagnosed sleep apnoea. Finally, a time will be scheduled within the next two days to set up the hypoxic generator, and the hood at the participant's home.

### *Intervention*

[figure not shown]
Participants will undertake 10 days of moderate home-based overnight normobaric hypoxia (FIO2 = ~0.155), and a sham hypoxia intervention (FIO2 = 0.2093) using hypoxic 'pillow tents' in a random order. The use of pillow tents rather than whole body tents was based on patient and public involvement (PPI) consultations. Participants will wear an SpO2 monitor at all times within the tent that will sound an alarm if SpO2 falls too low. If it sounds, participants will remove the hood (so that they breathe ambient air) and leave it off for the remainder of the night. An independent medical officer will decide if the participants can remain in the trial. The O2 fraction will be set by the researcher and participants instructed not to change the settings. Finally participants will be asked to maintain a diary of the time spent in the tent. Finally, participants will be asked to record a dietary diary and photograph meals in order to try and replicate it in both conditions. Participants will then undertake the alternative condition. The cross-over conditions will be separated by a minimum 4 week wash out period. During the intervention, as well as recording safety information (ie. SpO2) we will ask participants to wear a continuous glucose monitor (CGM) sensor (Abbott Diabetes Care Inc., Alameda, CA, USA) on the anterior portion of the upper arm with a small adhesive patch. These sensors will be worn for 14 days to determine free-living glycaemic control, in addition to a wrist-worn accelerometer (GENEActiv, Activinsights, Kimbolton, Cambridge, UK) to assess baseline habitual physical activity (PA) and sleep [32] (see details below in section 10.4).

*Visit 2, 3, 4 and 5 (approx 2.5 per visit)*

Visits 2-5 are identical in nature. Visits 2 and 4 are baseline visits before each arm of the crossover (i.e. the intervention). Visits 3 and 5 are following the 10 day hypoxic or sham exposures to assess the outcomes. An OGTT, body composition and venous blood samples and a stool collection will occur on each visit. After visit 3 there will be a 4 week washout out period. Visit 4 is necessary to ensure participants are back to baseline. During this visit, if anyone has had a respiratory tract infection or infectious disease in between visits, the hypoxic screening and lung function tests will be repeated. During visit 3, a new CGM sensor will be secured and accelerometer worn and a home visit for set-up will be re-booked. At the end of visit 5, another CGM and accelerometer will be affixed to the participants to check how long the effects of the intervention take to decay.

Urine collection is critical for our metabolomics analysis. In order to look for trends across time and between conditions we will need to collect urine before, during and after the intervention. Participants will be asked to collect a small urine sample for 2 days before the intervention starts, for each day of the intervention and for 2 days following the intervention. Participants will be provided with instructions on how to collect a mid-flow urine sample and how to safely store the samples until they are collected.

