## 7. STUDY DESIGN

### 7.1 Summary of Study Design

Single blind, randomized, balanced, crossover design study (i.e. participants will undergo both the hypoxia and sham conditions and will be blinded to the conditions in which they are in).

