### 7.2 Primary and Secondary Endpoints/Outcome Measures

#### *Primary outcome measure*

Post-intervention (sham vs hypoxia) area under curve for venous blood [glucose] during a 2 hour OGTT.

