### 14.2 Analysis of Endpoints

All data will be tested for normality using the Shapiro-Wilk test. For normally distributed data, paired samples t-tests will be used to assess differences pre and post hypoxic exposures for; blood [glucose] (AUC and peak), insulin sensitivity, eHSP70, IL-6, leptin, ghrelin, TNFa, SOD, HIF-1 $\alpha$  HR, PA and sleep efficiency. For non-parametric data Wilcoxon-Signed rank test will be used for pairwise comparisons. Repeated measures one-way analysis of variance (ANOVA) will be used to identify differences between conditions for SpO2 and [glucose] across time from the CGMs. Mauchly's test of sphericity will be used to determine if any data violated the assumption of spherical data. If violated, sphericity will be accounted for using the Greenhouse-Geisser correction. Where significant differences are observed ( $P < 0.05$ ), post-hoc tests will be performed using LSD pairwise comparisons. Effect sizes will be reported as partial eta squared ( $\eta^2_p$ ) (small = 0.01; medium = 0.06; large = 0.14) [33].

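### Visit 4 is meant to confirm washout, but the plan never compares it with visit 2 and the declared primary endpoint leaves it out, so any persisting hypoxia effect could shrink the estimate unnoticed

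*Combined protocol and SAP*

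**What the plan says.** Section 7.1 describes a "Single blind, randomized, balanced, crossover design study". In Section 10, under Intervention, the protection against carry-over is time: "The cross-over conditions will be separated by a minimum 4 week wash out period". The same section states that "Visits 2 and 4 are baseline visits before each arm of the crossover" and that "An OGTT, body composition and venous blood samples and a stool collection will occur on each visit", so glucose AUC and body composition are available before and after each condition. Visit 4 has a stated purpose: "Visit 4 is necessary to ensure participants are back to baseline". The only contingency given for visit 4 is repeat hypoxic screening and lung function tests after an intervening infection.

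The primary outcome in Section 7.2, repeated in the synopsis, is "Post-intervention (sham vs hypoxia) area under curve for venous blood [glucose] during a 2 hour OGTT". That contrast uses visits 3 and 5. Section 14.2 describes something else for glucose AUC: "paired samples t-tests will be used to assess differences pre and post hypoxic exposures for" a list that includes AUC. Season, in Section 9, is the only covariate named anywhere.

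The protocol treats the duration of effect as an open question. Sensors are fitted after visit 5 "to check how long the effects of the intervention take to decay".

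**The concern.** A second baseline visit is justified as the check on washout, yet the plan contains no comparison, tolerance or consequence for it. The declared endpoint would treat the post-sham value as clean in participants who had hypoxia first. If some glucose-lowering effect were still present, the sham value would be too low in that sequence and the hypoxia-sham difference would move toward zero.

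The protocol's own reasoning makes persistence worth checking. It expects weight loss, links weight loss to glycaemic control (Section 4), and does not explain why 4 weeks is long enough. Section 20 says the effect sizes and confidence intervals will be used to power a definitive trial, so a shrunken estimate would carry forward into that calculation.

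**Working it through.** **Which visits enter which test**

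- Section 7.2 endpoint: hypoxia-first participants contribute visit 3 (hypoxia) and visit 5 (sham); sham-first participants contribute visit 5 (hypoxia) and visit 3 (sham). Visits 2 and 4 do not enter.
- Section 14.2 test, before versus after hypoxia: hypoxia-first participants contribute visits 2 and 3; sham-first participants contribute visits 4 and 5. Here visit 4 is used, and hypoxia carry-over cannot enter, but sham is left out, so this test does not estimate the declared endpoint.

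**The plan's own figure.** The synopsis requires 13 subjects to detect 1 SD with alpha 0.05 and 80% power. Taking the SD as that of the within-participant difference, a two-sided paired t-test needs 10, and 13 gives 91% power. The plan does not say which SD is meant. The figure of 13 is on the safe side and is not at issue here. With 23 recruited and 15% dropout, 23 x 0.85 = 19.6, or about 19 completers.

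**Size of the possible bias.** Let the true effect be tau, and let a fraction c persist to visit 5 in hypoxia-first participants. With equal sequences the estimate is [tau + tau(1 - c)]/2 = tau(1 - c/2).

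- c = 0: no shrinkage
- c = 0.2: 10%
- c = 0.5: 25%

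Simulated power, for a true effect of 1 SD of the difference:

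- 13 participants (6 hypoxia-first): 91% at c = 0, 83% at c = 0.25, 70% at c = 0.5
- 19 participants: 98%, 95% and 87%

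If a shrunken estimate were used to size the next trial, its sample size would be multiplied by 1/0.9² = 1.23 at c = 0.2 and by 1/0.75² = 1.78 at c = 0.5.

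**What baseline adjustment does.** Regress D (post-hypoxia minus post-sham AUC) on X (the matching baseline difference). Let rw be the correlation between baseline and post values within a period, and rb the correlation between periods. Then Var(D) = Var(X) = 2(1 - rb) and Cov(D, X) = 2(rw - rb), so the slope and the correlation both equal b = (rw - rb)/(1 - rb). The large-sample variance factor is 1 - b². Estimating the slope multiplies it by (n - 2)/(n - 3), which is 10/9 = 1.111 at n = 12 and 18/17 = 1.059 at n = 20. With no carry-over:

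- rw 0.80, rb 0.70: b = 0.33; factor 0.889 x 1.111 = 0.988 to 0.889 x 1.059 = 0.941. Variance falls about 1% to 6%.
- rw 0.85, rb 0.70: b = 0.50; 0.75 x 1.111 = 0.833 to 0.75 x 1.059 = 0.794. Variance falls about 17% to 21%.
- rw = rb: b = 0; 1.111 to 1.059. Variance rises about 11% to 6%.

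If the same residual is present at visits 4 and 5, the mean of X is -c·tau/2. Reading the effect at X = 0 then gives tau[1 - (c/2)(1 - b)], so a fraction b of the bias is removed. At c = 0.2 the 10% shrinkage becomes 10% x 0.67 = 6.7% or 10% x 0.5 = 5%, and stays near 10% if the correlations are equal. Reading the effect at the mean of X would remove none of it.

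**Why not subtract baselines.** With equal correlations r, Var(D) = 2(1 - r) becomes 4(1 - r), which is double. Power at n = 13 falls from 91% to 65%, and 80% power needs 18. If the residual fades between visits 4 and 5, subtraction also overstates the effect.

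**How much visit 4 minus visit 2 can show.** With 19 completers, and taking the SD of that change as the SD used for the effect, a comparison between sequences has power of about 8% if 25% of the effect remains at visit 4, 17% if 50% remains, and 51% if all of it remains.

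**The case against.** Carry-over is hypothetical. Visit 5 in a hypoxia-first participant falls at least 28 + 10 = 38 days after a 10-night exposure, the washout is a minimum that may run longer, and nothing in the documents shows an effect lasting that long. This stands: a reader might infer that hypoxia effects do dilute the result, but the documents support only that they could.

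A reader might also infer that participants enter period 2 whatever visit 4 shows. The protocol does not say so; it states no rule, which is a gap and not a policy. Nor is it right that visit 4 has no analytic role anywhere, since the test written in Section 14.2 uses it as the starting value for sham-first participants. The mismatch between Sections 7.2 and 14.2 therefore has to be settled first, and the dilution argument applies only to the Section 7.2 contrast.

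The remedy is also limited. The correlations are assumed, for an AUC that Section 10.4 bases on samples at 0 and 120 minutes; precision may get worse; and the visit 4 comparison has little power. In a self-described pilot one could reasonably ask only for a descriptive table. These limits stand. They do not remove the main point: the visit is scheduled for a purpose the plan never carries out. The sensor secured at visit 3 is worn for 14 days, so it cannot reach visit 5, and no analysis of washout data from it is described.

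**Conclusion.** The point holds as a gap with a cheap improvement, not as a demonstrated bias. The plan assigns visit 4 the task of confirming washout, never compares it with visit 2, and leaves it out of the declared primary contrast. If carry-over exists, shrinkage is c/2 under balanced sequences: 0% at c = 0, 10% at 0.2 and 25% at 0.5, with c unknown.

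Baseline adjustment is worth having but should not be oversold. At 12 to 20 participants its effect on variance runs from about a 21% reduction to an 11% increase. It removes about a third to half of any bias under the assumed correlations (0.80 or 0.85 within a period, 0.70 between periods), and almost none if the two correlations are equal.

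**What to change.** 1. In Section 14.2, make the primary test hypoxia versus sham post-intervention AUC, so that it matches Section 7.2.
2. Regress the within-participant difference in post-intervention AUC on the difference in period baselines (visit 2 for period 1, visit 4 for period 2), and read the effect at zero baseline difference. Do the same for body mass, which Section 14.2 does not currently list. Do not simply subtract baselines.
3. Report visit 4 minus visit 2 with a 95% CI, separately for hypoxia-first and sham-first participants, as descriptive evidence on washout. Do not use it as a pre-test to choose the analysis.
4. In Section 10, replace the claim that visit 4 will ensure return to baseline with: *to measure, and adjust for, any residual difference from baseline*.

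The cost is analysis wording and one degree of freedom; every measurement is already scheduled. The downside is a possible variance increase of about 6% to 11% if the within-period and between-period correlations turn out equal, and incomplete removal of any carry-over bias.

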### **Continuous glucose monitoring (CGM)**

The sensors (Abbott Diabetes Care Inc., Alameda, CA, USA) will be fixed to the anterior portion of the upper arm with a small adhesive patch. These sensors will be worn for 14 days to determine free-living glycaemic control.

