### **Habitual Physical Activity and Sleep (accelerometry)**

Physical activity (PA) and sleep will be assessed using wrist-worn accelerometers (GENEActiv, Activinsights, Kimbolton, Cambridge, UK). These devices have previously been validated for use in healthy adult populations (7) and are extensively used in clinical studies. The GENEActiv accelerometers will measure triaxial movement acceleration in gravity (g) units ( $1\text{ g} = 9.81\text{ m/s}^2$ ) at a frequency of 100Hz continuously over a period of 7 days. The Euclidean norm (magnitude) of signals from the three axes minus 1 g (with negative numbers rounded zero) will be used to quantify acceleration due to movement in mg ( $1\text{ mg} = 0.00981\text{ m/s}^2$ ) (33). Following the measurement periods, data will be downloaded using manufacturers software and processed in R (R Core Team, Vienna, Austria) using the open source GGIR software package (<http://cran.r-project.org>) following completion of the study. Previously validated acceleration threshold values (in healthy adults) will be used to quantify the time (minutes/day) spent on average in each intensity category: total PA, and separately for light, moderate, vigorous intensities and the composite category moderate-vigorous PA (MVPA). To facilitate comparison with current national PA guidelines PA, average MVPA accumulated in bouts of at least 10 minutes will also be calculated.

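### The CGM sensor and accelerometer fitted at visit 3 stop recording before the second condition starts, and the available text names no fitting at visit 4

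*Combined protocol and SAP*

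**What the plan says.** The visit schedule is in Section 10 (Study Procedures), in the text on visits 2 to 5. Visits 2 and 4 are the baselines before each condition. Visits 3 and 5 close the conditions: "Visits 3 and 5 are following the 10 day hypoxic or sham exposures to assess the outcomes". The washout is placed next: "After visit 3 there will be a 4 week washout out period". The Intervention text makes this a lower limit: "The cross-over conditions will be separated by a minimum 4 week wash out period".

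The schedule then gives the purpose of visit 4 and the re-screening done there. Immediately after that comes the device instruction: "During visit 3, a new CGM sensor will be secured and accelerometer worn and a home visit for set-up will be re-booked". The next sentence moves to visit 5, where a further CGM sensor and accelerometer are fitted for a stated purpose, to see how long the effect takes to fade.

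Recording times are in Section 10.4. For CGM: "These sensors will be worn for 14 days to determine free-living glycaemic control". For the accelerometer: "at a frequency of 100Hz continuously over a period of 7 days".

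The Intervention text in Section 10 also says, without naming a visit, that participants wear a CGM sensor during the intervention, with a wrist accelerometer in addition.

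**The concern.** The only devices that the schedule names between the two conditions are fitted on the wrong side of the washout to record the second one. Two features suggest that they were meant for it. The sentence follows two sentences about visit 4, and it re-books the home set-up. Before the first condition, Section 10 schedules that set-up within two days of the screening visit, not a month ahead.

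Daily glucose excursions, physical activity and sleep quality are named secondary outcomes, and hypotheses 8 and 9 (activity maintained, sleep unaffected) rest on the accelerometer. Section 14.2 compares CGM glucose between conditions, which needs recordings in both. It tests physical activity and sleep efficiency before and after hypoxia, so a participant who receives hypoxia second needs a recording in the second condition. Section 10.4 drops anyone with fewer than four valid accelerometer days, and Section 14.3 skips missing points. Recordings that were never made could not be recovered at analysis.

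**Working it through.** The plan states no figure on this point, so there is none to reproduce. The check is a day count.

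**Inputs**
- Visit 3 = day 0 (end of the first condition; Section 10).
- Start of the second condition: day W, with W at least 28 (4-week minimum washout; Section 10, Intervention).
- Length of each condition: 10 days (Section 10, Intervention).
- Recording length L: 14 days for CGM, 7 days for the accelerometer (Section 10.4).
- F = day of fitting.

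**Formulas**
- Days of the second condition recorded = max(0, min(F + L, W + 10) − max(F, W)).
- Gap before the second condition = W − (F + L).

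**Fitted at visit 3 (F = 0), shortest washout (W = 28)**
- CGM: max(0, min(14, 38) − 28) = max(0, −14) = 0 of 10 days; gap 28 − 14 = 14 days.
- Accelerometer: max(0, min(7, 38) − 28) = max(0, −21) = 0 of 10 days; gap 28 − 7 = 21 days.

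A longer washout only widens the gap. At W = 35 the gaps are 35 − 14 = 21 and 35 − 7 = 28 days.

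**Fitted at visit 4 (taken as F = 28)**
- Exposure starting the same day (W = 28): CGM min(42, 38) − 28 = 10 of 10 days; accelerometer min(35, 38) − 28 = 7 of 10.
- Exposure starting one day later (W = 29; an assumption, by analogy with the two-day set-up window at screening): CGM min(42, 39) − 29 = 10 of 10; accelerometer min(35, 39) − 29 = 6 of 10.
- Two days later (W = 30, same assumption): CGM min(42, 40) − 30 = 10 of 10; accelerometer min(35, 40) − 30 = 5 of 10.

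Fitting at visit 4 therefore restores full CGM cover and still allows the four valid accelerometer days that Section 10.4 requires. One 7-day recording cannot span a 10-day condition wherever it starts, so the days it is meant to cover need stating in any case.

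**The case against.** A reader might infer that the second condition will have no CGM, activity or sleep data at all. The documents do not support that, for four reasons.

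- The Intervention text asks for device wear during the intervention, and it does so after describing both conditions and the washout. Staff could follow it and fit devices at visit 4.
- No fitting at visit 2 is named either. If silence about a visit meant no data, the first condition would have none, which is plainly not intended.
- Visits 3 and 5 are the two post-exposure visits, and devices are fitted at both. The visit 3 wear could be a follow-up of decay after the first condition, like the one stated for visit 5.
- The participant-flow key lists CGM and accelerometer, and the contents list a schedule of procedures and a flow chart as appendices. The diagram and those appendices are not in the text available for this review, and they may show a visit 4 fitting.

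All four stand against the stronger claim, but none removes the need for an edit. If visit 3 is a slip, it needs correcting. If it is a decay wear, that purpose and the visit 4 fitting are both unwritten. If the diagram shows a visit 4 fitting, the sentence must be reconciled with it. The statement that visits 2 to 5 are alike does not settle the matter: the procedures then listed for every visit are the OGTT, body composition, blood and stool, and the devices are assigned separately.

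A reader might also put a price on the loss by supposing that CGM falls back to a parallel comparison within the first condition. With 20 completers (23 × 0.85 = 19.55, rounded) and 10 per sequence, the standard error would be √(2/10) = 0.447 SD. The crossover value, √(2(1 − r)/20), is 0.224 SD at r = 0.5 and 0.173 SD at r = 0.7, giving ratios of 2.0 and 2.6. The arithmetic is right, but the correlations and the 20 completers are assumptions, and the fallback arises only if no devices are fitted at visit 4. These ratios are not the size of the finding.

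Nor does Section 14.2 compare activity and sleep between conditions. It does that only for SpO2 and CGM glucose.

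**Conclusion.** The point holds as a conflict within Section 10, and between it and the recording times in Section 10.4. Devices fitted at visit 3 record 0 of the 10 days of the second condition and finish at least 14 days (CGM) and 21 days (accelerometer) before it. That result rests only on the protocol's own figures.

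That visit 4 was meant is an inference from the sentence's position and the home set-up booking. The consequence is conditional. If the visit 3 instruction were followed and nothing were fitted at visit 4, the between-condition CGM comparison would lack second-condition data, and activity and sleep would go unrecorded in that condition. For participants who receive hypoxia second, there would then be no recording during hypoxia.

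The primary endpoint, glucose AUC in the OGTT, is untouched. The change is still worth making: the loss could not be repaired afterwards, and the correction is close to free.

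**What to change.** Amend the visit 3 sentence in Section 10 so that a new CGM sensor and accelerometer are fitted at visit 4, before the second condition, in the same way as before the first. Name the fitting visit for the first condition too. For each device, state the days it covers relative to the start of exposure, including which part of the 10-day condition the 7-day accelerometer recording is meant to capture. Check the flow diagram and schedule of procedures against the amended text.

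If a wear from visit 3 is also wanted to follow decay after the first condition, describe it separately with its own purpose. It would give participants who receive hypoxia first the same follow-up that the visit 5 wear gives those who receive it second.

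Cost: none if the fitting moves from visit 3 to visit 4. If both wears are kept, at most one extra sensor per participant, or 23 × 1 = 23 sensors at the planned sample size.
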